7.7 Imputation of Dates

If partial dates occur, the convention for replacing missing dates for the purpose of calculating derived variables is as follows:

- Missing day is imputed as the 15th of the month.
- In 12-month follow-up forms and chart reviews, missing month is imputed as 12 months from the patient's enrollment into the study.

Missing year is imputed as the year the practice enrolled the participant for baseline forms and the following year for 12-month follow-up forms.

7.8 Laboratory Reporting

No safety laboratory values are collected in the CAPTURE study.

8 Sample Size

8.1 Primary Objectives

Aim 3: Define the impact of CAPTURE information provided to clinicians in identifying and managing patients with respiratory symptoms (CAPTURE+) across a broad range of primary care settings.

8.2 Practice Behavior in Sites With Vs Without Capture Education and Patient Level Capture Data Provided

Primary Hypothesis 3: Sites where basic COPD and CAPTURE education are provided to clinicians, along with patient level CAPTURE data, will have a higher probability than control sites (i.e., those receiving only basic COPD education) of meeting the composite endpoint in their CAPTURE+ patients within 12 months of baseline.

From medical record review and follow-up patient survey responses, the composite endpoint is met if one of the following is recorded: 1) referral for or completion of clinical spirometry testing, 2) new clinical diagnosis of COPD, 3) newly prescribed respiratory medication (long acting bronchodilator or anti-inflammatory for respiratory condition), 4) referral to a specialist for respiratory evaluation/ treatment, or 5) referral for or completion of pulmonary rehabilitation.

The study will enroll 50 CAPTURE practices and 50 control practices; each practice will enroll 50 patients (for a total of 5,000 patients). We project that within each practice there will be at least five patients previously undiagnosed with COPD who have a CAPTURE+ screening result. The primary analysis will be to compare the average proportion of CAPTURE+ patients per practice that meet the composite endpoint in the two intervention arms. For power and sample size computations, this is a cluster randomized trial of n=50 clusters (practices) per intervention arm with 5 CAPTURE+ patients per cluster (practice). The primary power calculation is based on comparing the average cluster sample proportion (average proportion of CAPTURE+ patients per practice meeting composite endpoint) between intervention arms. Table 5 displays power for a two-sample test comparing average cluster sample proportions, accounting for possible intra-cluster correlation coefficient (ICC) values of 0.05, 0.10 and 0.15 that are typically seen in cluster randomized trials of behavioral interventions

(<https://www.abdn.ac.uk/hsru/research/research-tools/study-design/>). These calculations assume a type I error of 5% and that the control arm meets the composite endpoint in 5% of CAPTURE+ patients, and the CAPTURE arm meets the composite endpoint in higher percentages (columns of Table 5). There will be variability in the actual number of CAPTURE+ patients per practice. It is standard practice to inflate the number of needed clusters by 12% to account for this extra source of variability. Therefore, our power calculations are based on 44 clusters per intervention arm.

9 General Analysis Considerations

| | | | | | |
|---|-------|------|------|-------|-------|
| Overall power to detect a difference in rate of meeting primary endpoint in CAPTURE group (50 practices/cluster) vs usual care (50 practices/cluster), assuming 5% performance rate in usual care; 50 patients total / practice; assuming 10% prevalence gives 5 CAPTURE+/practice. | | | | | |
| Improvement over usual care | +7.5% | +10% | +15% | +25% | +50% |
| ICC=0.05 | 0.72 | 0.89 | 0.99 | >0.99 | >0.99 |
| ICC=0.10 | 0.65 | 0.84 | 0.98 | >0.99 | >0.99 |
| ICC=0.15 | 0.59 | 0.79 | 0.97 | >0.99 | >0.99 |

9.1 Timing of Analyses

The final analyses will be performed after

- (1) All 100 practices and 5000 participants have been enrolled
- (2) Participants selected for follow-up have completed their 12-month data assessments or been lost-to-follow-up
- (3) Chart review has been completed for those selected for follow-up
- (4) All corresponding data have been entered, cleaned, locked and unblinded as per SABER SOPs.

This SAP document was finalized and approved prior to the double-blind database lock and unblinding.

9.2 Blinded Data Review

Prior to database lock and the start of any formal analyses, blinded data reviews will be completed, including summary statistics of key variables. This will allow the data for key variables to be examined to identify unusual values that need to be queried and patterns of missing values. In addition, the data reviews will allow the Executive and Publication Committees to assess the format of the data presentations. Note that blinded data reviews incorporate real data but random intervention assignment (i.e., investigators do not receive data summarized by actual intervention group, rather they review data on two randomly formed groups). All decisions will be made and documented in this SAP document prior to unblinding and database lock.

9.3 Analysis Populations for the Cluster-Randomized Clinical Trial (Aim 3)

All enrolled practices will be used in descriptions of practice characteristics. Because the CAPTURE study involves a cluster randomized design, with the intervention given at the cluster level, we have natural intent-to-treat populations for analysis at the practice level. That is, patient and practice outcomes will be ascribed to the assigned intervention group for that practice. We will not define a per-protocol analysis population as part of this study. Protocol deviations will be described, but not used to adjust analysis populations inappropriately. The safety population is all patient participants selected for follow-up as part of the cluster-randomized trial described in Aim 3 of the CAPTURE protocol.

There are eight analysis populations:

- 1) CAPTURE + (Primary Analysis Population)
- 2) CAPTURE –
- 3) Spirometrically defined COPD
- 4) Clinically Significant COPD
- 5) Mild COPD
- 6) No COPD
- 7) Preserved ratio, impaired spirometry (PRISm)
- 8) Symptomatic non-obstructed (SNO)

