Basic COPD and CAPTURE specific education will use an interactive, web-based education program which will be provided to all practice personnel, including physicians, nurse practitioners, physician assistants, nurses, medical assistants, clerical staff and administrative staff. Practitioners at sites randomized to the CAPTURE+COPD education intervention will receive the CAPTURE score from the central study coordinators soon after the baseline assessments have been completed.

Addressing Aims 1 and 3 will include a baseline visit for all participants and for Aim 3 longitudinal follow-up over 12 months for a predefined cohort of participants. Determination of the participants included in the longitudinal follow-up cohorts will be made after the baseline visit.

Baseline Data

Practices and/or study staff will pre-screen patients according to local guidelines to identify potential participants based on the following criteria: no prior COPD diagnoses, between 45 and 80 years old, and speak and read either English or Spanish. The timing of the pre-screening and the method to approach these patients for participation in the study (e.g., at the next outpatient visit, via telephone) will be flexible, depending upon site recruitment preferences. Patients who are eligible based on the pre-screening questions and agree to participate in the study will sign informed consent. After signing the consent, they will complete the CAPTURE questionnaire, PEF testing, spirometry testing, other respiratory questionnaires, and provide past medical history and demographic information. Local/PBRN study coordinators for each of the 7 PBRNs will perform the study procedures and record baseline information into the electronic data capture (EDC) system.

The EDC system will calculate a CAPTURE score for each participant, based on his/her CAPTURE questionnaire answers and PEF measurement. A binary score (positive or negative CAPTURE) will be emailed to the central study coordinator only for participants randomized to CAPTURE+COPD education intervention practices. The coordinator will communicate this information to these practitioners. Practitioners at sites randomized to the COPD education only intervention will be blinded to CAPTURE scores. Practitioners in both intervention arms will be blinded to research spirometry results.

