| Preserved ratio, impaired spirometry (PRISm) | Participants without spirometrically defined COPD who have post-bronchodilator $FEV_1 < 80\%$ predicted. Among participants who do not complete post-bronchodilator spirometry and have pre-bronchodilator $FEV_1/FVC \geq 0.7$, those with $FEV_1 \geq 80\%$ predicted will be considered not to have PRISm and those with $FEV_1 < 80\%$ predicted will be considered to have undetermined PRISm status in primary analyses. |
| Symptomatic non-obstructed (SNO) | Participants without spirometrically defined COPD and without PRISm who have a COPD Assessment Test score ≥ 10 . |

Longitudinal Follow-up

A pre-defined subgroup of enrolled participants, who meet any of the below criteria, will undergo longitudinal follow-up at 12 months:

1. CAPTURE+ participants, as defined above.
2. Participants who have spirometrically defined COPD, as defined above, or post-bronchodilator $FEV_1 < 80\%$ predicted at baseline. If post-bronchodilator spirometry is not completed, then pre-bronchodilator $FEV_1 < 70\%$ predicted will be considered to satisfy this criterion for follow-up.
3. A random sample of approximately 5% who do not meet criteria 1 – 2.

Participants who meet the criteria for follow-up will be sent notification/reminder letters within the first three weeks of enrollment and at three, six, and nine months. Patient-reported data will be collected by COPD Foundation via telephone, secure web-based server, or mail-based methodologies, based on participant preference.

Subject medical data will be collected from the medical record to assess for changes in practice-level care.

[figure not shown]

Figure 1

The hypothesis for Aim 3 is that sites where COPD and CAPTURE education and patient-level CAPTURE data are provided to clinicians will exhibit improved COPD diagnosis and COPD-related care compared to sites where COPD education is provided to clinicians.

7 Inclusion-Exclusion Criteria and General Study Population for Aim 3

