4. Pre-bronchodilator spirometry will be done for all participants. Post-bronchodilator spirometry will be performed for participants with abnormal spirometry ($FEV_1/FVC < 0.70$ or $FEV_1 < 80\%$ predicted) *If the participant has taken a bronchodilator within a 2-hour window of spirometry the spirometry will be considered post-bronchodilator and a pre-bronchodilator spirometry will not be done.
5. The 12-month assessment consists of patient reported data, collected by the COPD Foundation, and medical record review completed by site coordinators.
6. This will be completed in those that are smoking at V1.

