Then the overall parameter estimate \bar{Q} has variance estimated by

$$T = \bar{U} + \left(1 + \frac{1}{m}\right) B$$

A confidence interval and p-value for the test of whether the parameter is non-null will be computed from \bar{Q} and T based on a t distribution.

12 Safety Analyses

Safety data, including AEs and SAEs will be summarized descriptively overall and by treatment group for the safety population. Coding into organ system will be performed by the study chairs for AEs and SAEs. The following organ systems will be summarized: cardiovascular disorders, dermatological disorders, gastrointestinal disorders, hematological disorders, metabolic disorders, musculoskeletal and connective tissue disorders, neurological disorders, psychological disorders, pulmonary disorders, renal and urinary disorders, hepatobiliary disorders, and other disorders.

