12.2 Adverse Events

Descriptive summary statistics for adverse events (AEs) during the baseline visit will be reported. The number of AEs during baseline and the frequencies (number and percentage) of participants with one or more AEs will be summarized by treatment group and overall.

In accordance with clinicaltrials.gov reporting requirements, the following table summarizing adverse events is required and will be provided:

- Other (Not Including Serious) Adverse Events: A table of anticipated and unanticipated events (not included in the serious adverse event table) that exceed 5% within either treatment group, grouped by organ system, with number and frequency of such events in each treatment group.

The summary statistics will be produced in accordance with section 10.

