12.3 Deaths, Serious Adverse Events and other Significant Adverse Events

Descriptive summary statistics for serious adverse events (SAEs) during baseline will be reported. The number of SAEs during baseline and the frequencies (number and percentage) of participants with one or more SAEs during baseline will be summarized overall, by treatment group, and by body system.

A subject listing of all SAEs during baseline, SAEs during baseline causing study discontinuation, and deaths will be presented.

In accordance with clinicaltrials.gov reporting requirements, the tables below summarizing deaths and SAEs are required:

- All-Cause Mortality: A table of all anticipated and unanticipated deaths due to any cause, with number and frequency of such events in each treatment group.
- Serious Adverse Events: A table of all anticipated and unanticipated serious adverse events, grouped by organ system, with number and frequency of such events in each treatment group.

The summary statistics will be produced in accordance with section 10.

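### The SAP's safety population is limited to patients selected for 12-month follow-up, but adverse events are collected at the baseline visit in everyone enrolled, before that selection is made

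*SAP*

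**What the plan says.** SAP 9.3 defines the set: "The safety population is all patient participants selected for follow-up as part of the cluster-randomized trial described in Aim 3". The opening of SAP 12 applies it: "Safety data, including AEs and SAEs will be summarized descriptively overall and by treatment group for the safety population".

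The events are tied to baseline. SAP 12.2 begins: "Descriptive summary statistics for adverse events (AEs) during the baseline visit will be reported". The summaries in SAP 12.3 are likewise of SAEs at baseline, and its listing reads: "A subject listing of all SAEs during baseline, SAEs during baseline causing study discontinuation, and deaths will be presented". The schedules of activities in both documents (Protocol 1.3, SAP 7.5) mark adverse events at the baseline visit only.

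Exposure is universal. SAP 7.5, footnote 4: "Pre-bronchodilator spirometry will be done for all participants". SAP 7.6 has peak flow measured in every participant.

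Selection comes later. Protocol 4.1: "Determination of the participants included in the longitudinal follow-up cohorts will be made after the baseline visit". Under SAP 6.1 the selected patients are those who are CAPTURE+, those with abnormal spirometry, and a third group: "A random sample of approximately 5% who do not meet criteria" 1 or 2.

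**The concern.** The population and the data do not match. Everyone who attends the baseline visit is exposed to the procedures whose risks Protocol 2.3.1 names, and everyone's events are recorded there. The safety population then keeps only patients chosen afterwards, largely on symptoms and lung function. Patients not selected complete the study at that visit (Protocol 4.3), so for them the baseline visit is the whole safety record, and it would not be tabulated.

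What is at stake is the final descriptive reporting, including the ClinicalTrials.gov tables. Numerator and denominator would both be conditioned on characteristics measured at or after exposure. The rule in SAP 12.2 that lists non-serious events "that exceed 5% within either treatment group, grouped by organ system" would also be applied to this subset. The documents do not show which way the rates would shift.

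**Working it through.** The plan gives no size for the safety population, so there is no stated figure to reproduce. The check has two parts.

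**1. Population against data**

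| Step | Who | Where |
|---|---|---|
| Baseline visit with peak flow and spirometry | All enrolled | Protocol 4.1, 8.1; SAP 7.5, 7.6 |
| Albuterol | Those with FEV1/FVC < 0.70 or FEV1 < 80% predicted on initial testing | Protocol 2.3.1, 8.1; SAP 7.5 |
| AEs recorded and reported to the DCC | All with events at the baseline visit | Protocol 8.4.3, 8.4.4 |
| Selection for follow-up | CAPTURE+, abnormal spirometry, about 5% of the rest | SAP 6.1 |
| AE/SAE summaries | Selected patients only | SAP 9.3, 12 |

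No section defines a different population for baseline events. Albuterol recipients are better covered than others, because CAPTURE+ status or an abnormality that persists after bronchodilator leads to follow-up. Those missed are mainly CAPTURE- patients whose values became normal after albuterol.

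**2. How many are left out**

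Let c be the share of enrolees meeting follow-up criterion 1 or 2. About 5% of the others are sampled, so

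share of enrolees left out = 0.95 × (1 − c).

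Inputs for c:
- SAP Table 6 (March 2020): 663 + 750 + 431 + 280 + 468 + 446 = 3,038 patients; 15 + 15 + 9 + 6 + 11 + 12 = 68 practices; 3,038 / 68 = 44.7 patients per practice.
- SAP 13.1: 10 CAPTURE+ per practice (used in the power calculation) and roughly 2 spirometric COPD per practice.
- SAP 8.2: the design assumption of 5 CAPTURE+ among 50, or 10%.

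| c | Basis | Left out |
|---|---|---|
| 10% | Design assumption, CAPTURE+ only | 85.5% |
| 10 / 44.68 = 22.4% | March 2020, all COPD patients also CAPTURE+ | 73.7% |
| 12 / 44.68 = 26.9% | March 2020, no overlap | 69.5% |
| 40% | Assumed | 57.0% |
| 1 − 0.5/0.95 = 47.4% (about 21 per practice) | Value at which half are left out | 50.0% |
| 60% | Assumed | 38.0% |

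Values of c above 26.9% are assumptions. They allow for patients followed only because FEV1 is below 80% predicted, whose number the documents do not give. Two further groups would lower the share left out at any c: patients selected under the broader criteria in force before Amendment 2.0 and kept in follow-up (Protocol 14), and replacement controls, which SAP 7.5 footnote 3 still provides for. Neither can be quantified from the documents.

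**What the denominator does to a rare event.** With no events among n patients, the 95% upper bound on the rate is 1 − 0.05^(1/n). For 5,000 enrolled it is 0.06%. With c = 10%, the safety population is 5,000 − 0.95 × 4,500 = 725 and the bound is 0.41%. With c = 24% (12 of a planned 50 per practice), it is 5,000 − 0.95 × 3,800 = 1,390 and the bound is 0.22%.

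**The case against.** The strongest defence is scope. The SAP concentrates on Aim 3 and sets Aim 1 aside (SAP 4.1). Baseline spirometry and peak flow in all enrolees are Aim 1 assessments (Protocol 8.1), the Aim 3 intervention is clinician education and feedback, and SAP 12.1 measures exposure by intervention fidelity. Each aim has its own registry number, so an Aim 1 record might report baseline events in everyone. Protocol 8.4.3 also asks for AEs on study to be documented, which could explain a followed cohort. The SAE listing and the registry SAE table in SAP 12.3 do not repeat the restriction, and the table list in SAP 16 is not visible.

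Part of this stands. The serious-event listing can be read as covering everyone, which leaves SAP 12.3 in tension with the opening of SAP 12. The 95% figure is simply one minus the sampling fraction, and the share of all enrolees is uncertain. Few events are expected.

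The rest does not remove the mismatch. The SAP's own account of the trial includes every enrolee's baseline visit (SAP 4.1, 6.1), and SAP 9.3 includes CAPTURE- and No COPD populations. No AE collection is scheduled after baseline, and SAP 12.2 summarises baseline events only. A separate registry report or an unseen table specification cannot be assumed to override a stated rule.

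**Conclusion.** The concern holds as stated. Followed literally, SAP 9.3 and 12 drop about 95% of patients meeting neither follow-up criterion from the summaries of events those patients were exposed to and had recorded. As a share of all enrolees, the omission is about 69% to 74% on the March 2020 figures before counting low-FEV1 patients, and it remains at least half until c reaches about 47%. These shares rest on the memo's per-practice counts and a 5% sample; for a given c they are upper values, because of the earlier-criteria patients and replacement controls.

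The consequence is limited to descriptive safety tables. Baseline AEs still reach the DCC, SAEs still go to the IRB and DSMB, and no efficacy conclusion depends on these tables. The plan should be corrected, but the point does not threaten the trial's main result.

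**What to change.** In SAP 9.3 and 12, define the safety population for baseline AEs and SAEs as all enrolled participants who began any baseline study procedure, summarised by arm and overall. State that the 12.2 and 12.3 tables, the 5% listing rule and the SAE listing all use that population. Keep patients selected for follow-up as the denominator for 12-month deaths only, since only they are followed. A separate row for albuterol recipients is optional.

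The cost is SAP wording. No new data are needed, because baseline AEs are already on the CRF and at the DCC. SAP 9.2 calls for decisions to be documented before unblinding and database lock. If that point has passed, a dated clarification is enough for descriptive tables.

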9.4 Covariates and Subgroups

The effect of the CAPTURE intervention will be explored in predefined subgroups of interest with results tabulated (estimated difference in average proportion of CAPTURE+ patients per practice meeting composite endpoint between intervention arms by subgroup, corresponding 95% confidence interval and p-value) as well as displayed via forest plots. These analyses will proceed similarly to that described for the primary endpoint in section 11.1. Individual-level covariates used to define subgroups of interest are categorical age (45-59 years, 60-69 years, 70-80 years), gender (Male, Female), race (American Indian/Alaska Native, Asian, Native Hawaiian or Other Pacific Islander, Black or African American, White, Unknown or Not Reported), ethnicity (Hispanic/Latino, Non-Hispanic/Latino, Unknown or Not Reported), educational status (Less than High School Graduate, High School Graduate/GED, Vocational/Some College, College Degree, Professional/Graduate Degree, or Not Reported), insurance status (private, public, none), living arrangements (alone, not alone), employment status (working, not working, unknown), smoking status (Current, Former, Never), asthma history, baseline respiratory medications (short-acting bronchodilator, maintenance respiratory medication, or none), cardiac morbidity, COPD Assessment Test (CAT) score (10 or above versus less than 10), BMI (Below 25.0 [Normal/Underweight], 25.0-29.9 [Overweight], 30.0-39.9 [Obese], 40.0 and Above [Severely Obese]), as well as cohorts defined in section 6.1 (Spirometrically Defined COPD, Clinically Significant COPD, Mild COPD, No COPD by Spirometry, PRISm, and SNO). Practice level covariates include practice type (Part of large health system/ACO/similar, Part of academic medical center/health system, Federally Qualified Health Care Center, Independent practice, Other), location (Rural, Non-rural), being a residency site, having in-house spirometry, and number of MD/DO/NP/PA primary care clinicians (0-4, 5-9, 10 or More). Because of the possible impact of the SARS-CoV-2 pandemic on study outcomes, these analyses will be repeated in subgroups defined by whether the one-year follow-up period had entirely elapsed by March 19, 2020 (date when PBRNs paused study enrollment due to SARS-CoV-2); that is, the analyses will be repeated separately in the cohort with baseline visit completed on or before March 19, 2019, and separately in the cohort with baseline visit completed after March 19, 2019. Chart review and patient follow-up survey need not be completed by March 19, 2020 for a patient to be categorized as having pre-pandemic follow-up for this subgroup analysis.

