11.2 Secondary Efficacy Analyses

Secondary Analyses of Primary Outcome: The primary analysis as described in section 11.1 will be repeated in analysis populations 2-8 as given in section 9.3 overall and by subgroups described in section 9.4. For analysis population 1, the primary analysis as described in section 11.1 will be repeated in subgroups described in section 9.4.

In addition, multivariable GEE regression analyses will be conducted separately in populations 1-8 from section 9.3, where the primary composite outcome is modelled using individual and practice level predictors in addition to the CAPTURE intervention group. Interactions will be assessed.

Efficacy Analyses of Secondary Outcomes: All analyses in this section will be conducted (separately) for each study population 1 through 8 described in section 9.3 overall and by subgroups described in section 9.4.

We will use the GEE framework to study and describe each of the individual components of the composite outcome as they relate to the CAPTURE intervention group.

In the subset of patients who report being current smokers at baseline, we will study additional binary outcomes, such as incidence of physician counselling/recommendation to stop smoking, physician referral to a formal smoking cessation program, newly prescribed smoking cessation medication, and referral to a smoking quit line, individually and in a composite outcome that also incorporates the primary outcome components.

Multivariable GEE models will incorporate individual and practice level covariates into the analysis of individual components of the composite outcome. Model selection in multivariable secondary analyses will be based on statistical significance at the 0.05 level using GEE robust sandwich estimation of variability within clusters. Model fit will be checked by comparing observed versus predicted values within predefined subgroups of interest as given in section 9.4.

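### SAP 9.4 gives every subgroup level its own p-value but specifies no arm-by-subgroup interaction test for those tables and forest plots

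*SAP*

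**What the plan says.** - SAP 9.4 states the purpose: "The effect of the CAPTURE intervention will be explored in predefined subgroups of interest with results tabulated". Each subgroup gets the "estimated difference in average proportion of CAPTURE+ patients per practice meeting composite endpoint between intervention arms by subgroup, corresponding 95% confidence interval and p-value", and the results are also shown as forest plots.
- On method, 9.4 says: "These analyses will proceed similarly to that described for the primary endpoint in section 11.1". Section 11.1 is the identity-link GEE of the composite on arm, tested two-sided at 0.05. Run inside one level, it tests whether the effect in that level is zero.
- The factors run from patient characteristics, "Individual-level covariates used to define subgroups of interest are categorical age (45-59 years, 60-69 years, 70-80 years), gender (Male, Female" and so on, to practice characteristics such as "being a residency site, having in-house spirometry, and number of MD/DO/NP/PA primary care clinicians (0-4, 5-9, 10 or More".
- The set is then repeated by pandemic period: "the analyses will be repeated separately in the cohort with baseline visit completed on or before March 19, 2019", and likewise in the later cohort.
- SAP 11.2 extends it further. The primary analysis "will be repeated in analysis populations 2-8 as given in section 9.3 overall and by subgroups described in section 9.4", and the secondary outcomes are also analysed by subgroup.
- In SAP 11.2, "Interactions will be assessed" closes the paragraph on multivariable GEE models of the composite. Protocol 9.3.2 has the same sentence after its secondary GEE models. Neither names the variables, the test or the significance level, and neither refers to the subgroup tables.
- SAP 9.7 applies Bonferroni only to the five components of the primary endpoint. It makes no other adjustment and asks for caution in reading secondary and exploratory p-values.

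**The concern.** A p-value within a level answers whether there is an effect in that level. A subgroup table or forest plot is read to learn whether the effect differs between levels, and only a comparison between levels tests that. The planned display supplies the first kind of p-value many times over and the second kind nowhere.

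Two misreadings follow. If the intervention does nothing, a few levels will look positive by chance. If it works equally well everywhere, large levels will be significant and small ones will not, and the pattern will look as if some patients or practices do not benefit. At stake is what the trial appears to say about where CAPTURE screening changes care.

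**Working it through.** **The plan's own figures.** The documents give no subgroup count and no subgroup error rate. The nearest stated figure is the power table in SAP section 8. With k practices per arm, m CAPTURE+ patients per practice, p̄ the mean of p1 and p2, and d = p2 − p1:

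- effective n per arm = k·m / (1 + (m − 1)·ICC)
- power = Φ{ [d − 1.96·√(2p̄(1 − p̄)/n)] / √([p1(1 − p1) + p2(1 − p2)]/n) }

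At k = 44, m = 5 and ICC 0.10, n = 220/1.4 = 157.1. For 5% against 12.5%, 15% and 20%, power is 0.654, 0.843 and 0.983. The SAP states 0.65, 0.84 and 0.98.

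**Number of levels in SAP 9.4.**

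- Patient factors (14): age 3, gender 2, race 6, ethnicity 3, education 6, insurance 3, living arrangement 2, employment 3, smoking 3, asthma 2, respiratory medication 3, cardiac morbidity 2, CAT 2, BMI 4. Sum 44.
- Practice factors (5): type 5, location 2, residency 2, in-house spirometry 2, size 3. Sum 14.
- Total 58 levels in 19 factors. The six section 6.1 cohorts make 64.
- Dropping the four Unknown/Not Reported levels (race, ethnicity, education, employment) from the 64 leaves 60. Dropping the cohorts as well leaves 54.

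**If there is no effect anywhere** (0.05 two-sided per level, assumed to carry over from 11.1). Expected number significant = levels × 0.05, which does not require independent tests.

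- 64 × 0.05 = 3.2; 60 × 0.05 = 3.0; 58 × 0.05 = 2.9; 54 × 0.05 = 2.7.
- Adding the two pandemic cohorts: 3 × 64 = 192 tests, 192 × 0.05 = 9.6.
- The chance of at least one would be 1 − 0.95^64 = 0.96 if tests were independent. They overlap, so this is only a reference value.
- Simulation: 1,000 trials per scenario, 100 practices, ICC 0.10, an average of 5 or 10 CAPTURE+ patients per practice, a cluster-robust difference within each level, and subgroup shares assumed because the documents give none. The mean was 3.6 to 4.5 significant levels, the median 2 to 3, and the chance of at least one 0.82 to 0.94. The likely reason for the excess over 3.2 is robust variances in small cells.

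**If the effect is the same everywhere** (5% against 15%, ICC 0.10, 44 practices per arm, 5 patients each). Power within a level falls with its size:

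- Practice factor, half the practices: 22 × 5/1.4 = 78.6 per arm, power 0.55.
- Practice factor, a fifth of the practices: 8.8 × 5/1.4 = 31.4, power 0.26.
- Patient factor, half the patients: 44 × 2.5/1.15 = 95.7, power 0.64.
- Patient factor, a fifth of the patients: 44 × 1/1 = 44, power 0.34.

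For a practice factor split evenly, the two levels use different practices. The chance that exactly one is significant is 2 × 0.552 × 0.448 = 0.49, with no difference in effect. In the simulation at 5% against 15% with 10 patients per practice, about 41 of 63 estimable levels were significant and about 22 were not. Tests of heterogeneity flagged 0.9 of 19 factors on average.

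**With one interaction test per factor.** 19 × 0.05 = 0.95. Counting the cohorts as one further test gives 20 × 0.05 = 1.0. Six separate cohort contrasts would give 25 × 0.05 = 1.25.

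**The case against.** The strongest reply is that this is predefined exploration, shown with confidence intervals, with the lack of adjustment disclosed and caution requested in SAP 9.7. Protocol 9.1.2.2 also calls the secondary practice-behaviour analyses exploratory. Interactions are planned in 11.2, and 9.4 lists the covariates such models would use. Aim 3 in protocol 2.1 asks which characteristics are associated with care, and multivariable models address that.

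Much of this stands. A reader might infer that the plan replaces interaction tests with subgroup p-values, or that it will declare a subgroup effect whenever its own p-value is below 0.05. The documents support neither reading: interactions are to be assessed in some form, and no rule turns a within-level p-value into a claim. Nor does a confidence interval per level end the matter, since an interval that excludes zero carries nearly the same message as the p-value.

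What does not stand is that 11.2 already covers the need. Its interaction sentence concerns the multivariable models of the composite, leaves the terms open, and is not attached to the tables or forest plots. The subgroup analyses of the secondary outcomes have no such sentence. Caution in reading does not help when the relevant test is absent from the display.

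**Conclusion.** The point holds as a gap in specification. SAP 9.4 reports within-level p-values for about 58 to 64 levels and does not specify the test that would show whether effects differ.

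Its size depends on the truth. With no effect anywhere, about three levels are expected to be significant by chance in the main CAPTURE+ set, before the repetitions. It might be inferred that several false subgroups are to be expected in any case. That does not follow: if the intervention works throughout, the significant levels are not false, and the risk is a false impression of differing benefit.

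The counts come directly from SAP 9.4. The simulation and the half and one-fifth shares are assumptions. The primary analysis, its population and its power are unaffected, so this is a minor, worthwhile improvement.

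**What to change.** In SAP 9.4:

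- Keep the estimate and 95% confidence interval for each level, and drop the per-level p-value.
- Add one arm-by-subgroup interaction p-value per factor from the identity-link GEE, with several degrees of freedom where needed, printed beside the forest plot. A six-level factor needs five interaction terms, so state in advance how sparse levels are collapsed, and leave Unknown/Not Reported out of the test.
- For the section 6.1 cohorts, which overlap (clinically significant and mild COPD both lie within spirometrically defined COPD), use separate contrasts such as cohort against not in cohort.
- Cross-refer to the interaction sentence in 11.2, name the variables, and say whether the same rule applies to the secondary outcomes.
- State that any claim of differing effect rests on the interaction test and remains exploratory, because about one chance finding is still expected without a multiplicity rule.

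The cost is SAP wording and one extra fitted model per factor. The drawbacks are low power of interaction tests and possible fitting problems with an identity link in sparse cells. If the database is already locked, report this as a documented addition.
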